1.7 The Men’s Eating and Living (MEAL) Pilot Study

Based on the WHEL experience, we designed and implemented a pilot study of diet change in men with prostate cancer based on similar principles of behavior change: the Men’s Eating and Living (MEAL) Study (40-42). This randomized, controlled clinical pilot trial of 74 men, most with clinically localized prostate cancer, utilized the same diet-change intervention outlined in this application. To increase the number of change patients for evaluation, we randomized 2 patients to intervention for every one randomized to comparison. This trial was different from the WHEL study, in that we invited the spouse or significant other of the patient, and not just the patient, to participate in the diet counseling. The study demonstrated that diet change with telephone-based counseling results in increased vegetable intake and increased plasma carotenoid concentrations among men with prostate cancer.

Dietary changes: vegetables

Consistent with counseling targets, vegetable intakes in the intervention arm increased significantly at six months, while those in the control arm remained static (Table 1). Diet was measured by a series of three 24-hour recalls collected interactively via telephone interview. In the intervention arm, mean daily intakes of total vegetables, crucifers, tomato products and other vegetables increased by 76%, 143%, 292%, and 55%, respectively. The intervention emphasized vegetable, rather than fruit intake, and white potatoes and lettuce did not count. As a result, fruit, lettuce, and potato intake declined for experimental subjects (40-42). In the control arm, there were no significant changes in mean intakes of total vegetables, crucifers, tomato products, lettuce and potatoes, or other vegetables.

Table 1. Vegetable intake* at baseline and 6 months as assessed by 24 hour dietary recall in the Men’s Eating and Living (MEAL) Study

	Intervention n=45			Control n=23		
	Baseline	6 Months	Change	Baseline	6 Months	Change
Total vegetables	4.1	7.2	76%†‡	3.7	4.2	12%
Cruciferous vegetables	0.7	1.7	143%†‡	0.4	0.6	44%
Tomatoes	0.6	2.3	292%†‡	0.7	0.8	5%
Lettuce and potatoes	1.0	0.4	-58%†‡	0.6	0.6	-3%
Other vegetables	1.8	2.8	55%†	1.9	2.2	12%

*All intakes measured in servings per day

†Significant difference (p<0.05) between groups

‡Significant difference ($p < 0.05$) within groups

Dietary changes: non-vegetables

Intakes of whole grains and beans in the intervention group increased, while fat intake decreased; mean daily intakes of whole grains and beans increased by 28% and 95%, respectively, while fat intake decreased by 12% ($p < 0.05$). In the control arm, whole grain and fiber intakes decreased by 33% and 21%, respectively ($p < 0.05$), and there were no significant changes in fruit, beans, fiber, or fat intakes (data not shown) (40-42).

Plasma carotenoid concentrations

Consistent with increased vegetable consumption, carotenoid concentrations increased in the intervention but not in the control group (Table 2). At baseline, plasma total carotenoid concentrations of intervention and control participants were virtually the same. At six months, however, those of intervention and control participants, respectively, rose by 26% and 3% ($p = 0.02$). In the intervention group, α -carotene, β -carotene, lutein, and lycopene concentrations increased significantly, while those in the control group remained static ($p < 0.05$). Cryptoxanthin levels changed in neither group. That the changes observed were qualitatively larger than those observed in such prevention interventions as the Polyp Prevention Trial (69) suggests that this test of dietary intervention might be much more sensitive and powerful than either the Polyp Prevention Trial or the Women's Health Initiative (70).

Although the MEAL study was not strictly intended for AS patients, the patients on AS (53% of the study sample) experienced dietary change and plasma carotenoid results identical to those for the entire group (42). These data support the feasibility of implementing a larger clinical trial of a telephone-based diet intervention in men with prostate cancer treated with AS.

Our data, which include blood-based biomarkers, indicate that experimental subjects changed their diets, but that comparison subjects did not. Other data, including the Polyp Prevention Trial (71) and the Women's Healthy Eating and Living study (66), confirm that comparison subjects in diet intervention trials in general do not change their diets to nearly the extent that experimental subjects do.

Table 2. Plasma carotenoid concentrations at baseline and 6 months in the Men's Eating and Living (MEAL) Study

Carotenoid (mmol/L)	Intervention n=45			Control n=23		
	Baseline	6 Months	Change	Baseline	6 Months	Change
α -Carotene	0.17	0.23	33%‡	0.16	0.17	5%
β -Carotene	0.61	0.83	36%†‡	0.63	0.66	5%
Lutein	0.44	0.53	19%†‡	0.43	0.43	0
Lycopene	0.79	1.03	30%†‡	0.86	0.87	2%
Cryptoxanthin	0.19	0.17	-11%	0.17	0.18	11%
Total Carotenoids	2.21	2.79	26%†‡	2.24	2.32	3%

†Significant difference ($p < 0.05$) between groups

‡Significant difference ($p < 0.05$) within groups

MEAL: Program satisfaction

The response to the intervention was almost universally positive. In a very preliminary attempt to document the extent to which the participants experienced this program positively, we administered a limited questionnaire to 33 of the participants. We asked

them to describe their satisfaction on a 5-point scale, with 1 indicating strong dissatisfaction and 5 strong satisfaction. The responses were extremely positive; 31 of 33 rated their counselor a 5 for being prompt and convenient with sessions; 30 of 33 rated the counselor a 5 for listening; 32 of 33 rated the counselor a 5 for being easy to talk to; 29 of 33 rated the counselor a 5 for knowledge; 26 of 33 gave the counselor a 5 for being helpful; 25 of 33 gave the counselor a 5 for motivating them; and 24 of 33 gave the counselor a 5 for helping them to overcome barriers.

1.8 Study Design

In summary, these promising pilot data support the feasibility of a larger clinical trial of a telephone-based dietary intervention in men with prostate cancer treated with AS. The synthesis of these two aims-optimizing management of active surveillance patients through diet-represents a novel approach to this topic with a high potential for providing near-term patient benefits that would serve both the prostate cancer population and the broader public health. An adequately powered trial, focusing on diet as a primary form of intervention is needed.

CALGB 70807 is a randomized, phase III clinical trial designed to test this practical, diet-based intervention for prostate cancer in a broader clinical setting. Patients on AS will be randomized either to an intervention of centralized, telephone-based dietary counseling and structured dietary education or to a comparison control condition in which they receive the Prostate Cancer Foundation booklet entitled “Nutrition, Exercise and Prostate Cancer.” Study endpoints will include disease progression, incidence of treatment, and health-related quality of life.

1.9 Inclusion of Women and Minorities

Because prostate cancer occurs primarily in men above the age of 50, recruitment of participants for this study will focus upon men aged 50 years and older. Since women and children are not subject to prostate cancer, they will be excluded from this study. Efforts will be made to enroll individuals of all races and ethnic backgrounds, with the added goal of recruiting relatively high numbers of individuals of Hispanic origin and of African-American origin. The increased risk of prostate cancer and especially of lethal prostate cancer among African Americans makes it imperative that we secure adequate representation of African Americans in this study.

CALGB has a long history of effort to ensure adequate representation of minorities in all clinical trials, including prevention trials. The recent experience of the Selenium and Vitamin E Cancer Prevention Trial (SELECT) (80) is instructive: 29% of the CALGB participants were African Americans. In our MEAL pilot study, 12% of participants were non-white. Our goal with the full MEAL trial is for 29% of participants to be members of racial minorities, especially African Americans.

Racial Categories	DOMESTIC PLANNED ENROLLMENT REPORT				
	Ethnic Categories				
	Not Hispanic or Latino		Hispanic or Latino		Total
	Female	Male	Female	Male	
American Indian/Alaska Native	0	3	0	0	3
Asian	0	9	0	0	9
Native Hawaiian or Other Pacific Islander	0	1	0	0	1
Black or African American	0	53	0	1	54
White	0	381	0	16	397
More Than One Race	0	0	0	00	0

Total	0	447	0	17	464
-------	---	-----	---	----	-----

2.0 OBJECTIVES

2.1 Primary Objective

To determine if a telephone-based dietary intervention compared to no intervention will decrease clinical progression in AS patients.

2.2 Secondary Objectives

2.2.1 To compare the incidence of active treatment (surgery, irradiation, local ablation, or androgen deprivation) in AS patients receiving dietary intervention compared to no intervention.

2.2.2 To compare prostate cancer-related anxiety in AS patients receiving dietary intervention compared to no intervention.

2.2.3 To compare health-related quality of life in AS patients receiving dietary intervention compared to no intervention.

[See Section 10.0 for correlative science objectives.]

3.0 ON STUDY GUIDELINES

The following guidelines are to assist physicians in selecting patients for whom protocol therapy is safe and appropriate. Physicians should recognize that the following might increase the risk to the patient entering this protocol:

- Patients with medical conditions which, in the opinion of the treating physician, would make this protocol unreasonably hazardous for the patient should not be enrolled. Such conditions may include uncontrolled chronic diseases (including uncontrolled diabetes mellitus, cardiac disease, ulcerative colitis, and Crohn’s disease); or psychiatric illness/social situations that would limit compliance with study requirements and/or prevent the patient from giving informed consent.
- Intolerance of cruciferous vegetables.
- Unwillingness to adopt a vegetable-intense diet.

4.0 ELIGIBILITY CRITERIA

4.1 Preregistration Eligibility

4.1.1 Histologic Documentation: The initial biopsy showing diagnosis of prostate cancer should be used for the purposes of determining eligibility. However, if a subsequent biopsy performed before patient enrollment shows that the patient is ineligible, he may not be enrolled to the study. Eligible patients must meet all of the following criteria:

- Biopsy-proven (consisting of ≥ 10 tissue cores) adenocarcinoma of the prostate diagnosed within 24 months prior to pre-registration.
- $< 25\%$ of biopsy tissue cores positive for cancer.
- $\leq 50\%$ of any one biopsy tissue core positive for cancer.
- Clinical stage $\leq T2a$.
- Patients who have prostate cancer with distant metastases are not eligible.

NOTE: If a patient undergoes a transurethral resection of the prostate (TURP) for benign prostatic hyperplasia (BPH), and prostate cancer is diagnosed incidentally from the TURP specimen, eligibility for CALGB 70807 cannot be determined from the TURP specimen. However, if the patient subsequently undergoes a minimum 10-core prostate biopsy within 2 years of prostate cancer diagnosis from the TURP, and

prostate cancer is detected in the biopsy specimen and meets the requirements above, the patient is eligible for this study. If prostate cancer is not detected in the biopsy specimen, the patient is not eligible.

- 4.1.2 Prior Treatment:** Patients who have had prior treatment for prostate cancer by surgery, irradiation, local ablative (i.e. cryosurgery or high-intensity focused ultrasound) or androgen deprivation therapy are not eligible.
- 4.1.3** Patients who have had a history of non-cutaneous malignancy (other than non-melanoma skin cancer) in the previous 5 years are not eligible.
- 4.1.4 Language:** Patients must be able to read and comprehend English language text and be able to understand spoken English over the phone.
- 4.1.5** Life expectancy of at least 3 years.
- 4.1.6** Patients who are currently taking vitamin supplements including lycopene and beta-carotene are eligible.
- 4.1.7** Patients receiving treatment with 5-alpha reductase inhibitors (e.g., finasteride, dutasteride) within 90 days prior to preregistration are not eligible. Treatment with these agents during the protocol intervention is not permitted.
- 4.1.8** Patients who are currently taking coumadin are not eligible.
- 4.1.9** Participants will be men aged 50 to 80 years.
- 4.1.10** For men ≤ 70 years, biopsy Gleason score ≤ 6 ; for men > 70 years, biopsy Gleason score $\leq (3 + 4) = 7$.

4.1.11 Required Initial Laboratory Values:

- Serum PSA < 10 ng/mL

NOTE: Baseline PSA for determination of eligibility must be measured after discontinuation of any 5-alpha reductase inhibitors.

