7.0 REQUIRED DATA

Guidelines for Pre-Study Testing

To be completed within 3 months before preregistration

- Baseline PSA, history and physical, DRE

To be completed within 24 months before preregistration

- Prostate Biopsy

	Preregistration	Run-in	Month*							
			3	6	9	12	15	18	21	24
Test and Observations										
History and Physical	X			X		X		X		X
Height†	X									
Weight†	X			X		X		X		X
DRE	X					PRN				PRN
Diet Recall		A				A				A
Labs and Staging										
PSA	X		X	X	X	X	X	X	X	X
QOL Instruments										
Personal Habits Questionnaire	B									
MAX-PC	B			X		X		X		X
Nutritional Self-Efficacy	B			D		D		D		D
I-PSS	B			X		X		X		X
EPIC-26	B			X		X		X		X
FACT-P	B			X		X		X		X
MEAL Counseling Evaluation						D				D
Sample Submission										
Plasma for Carotenoid Analysis	C					X				X
H & E biopsy slides‡	C									X(1)
Correlative Study	See Section 6.2.									
Serum										
Whole Blood										
Unstained Slides‡										

A To be conducted by UCSD staff.

B To be administered to all patients at the pre-registration visit and submitted after the patient is registered to the study.

C To be collected for all patients at the pre-registration visit and submitted after the patient is registered to the study.

D To be administered to patients randomized to Arm A only.

* Clinic visits may be done within +/- 2 weeks of the scheduled 3-, 6-, 9-, etc. month visit. These visits are to be scheduled from the date of randomization.

† Refer to Section 8.1 for height and weight measurement instructions.

‡ Slides should be from the initial biopsy showing diagnosis of cancer.

1 24-month biopsy is not required for patients who have started definitive treatment (e.g., prostatectomy or radiation therapy).

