8.4 Clinic Visits

PSA Measures (Every 3 Months)

Serum PSA levels will be measured at baseline and at every 3 months thereafter. PSADT will be calculated as \log_2 divided by the slope (the least squares estimator) of \log (PSA) observations over time using the last three PSA measurements (44, 83, 100). An example of a PSADT calculator can be found at www.ASURE.ca.

History & Physical (Every 6 Months)

Participants will be evaluated in a urology clinic at initial assessment and every 6 months thereafter as per typical AS protocols and current standard of care (2-4, 11, 13). Patients must be weighed and their height measured according to the instructions in Section 8.1. Urological evaluations will be conducted by the GU Investigator or appropriate designee (e.g., medical oncologist, PA, NP) at each site. The baseline visit will include a DRE to confirm clinical stage. Since PSA and biopsy changes are much more sensitive for detecting clinical progression than changes in prostate examination among patients on AS (11), subsequent DRE will be performed at the discretion of the individual urologist. These results will not be used to define progression.

Prostate Biopsy (24 Months)

Prostate biopsy will be performed by the treating urologist at 24 months with a minimum of 10 tissue cores obtained utilizing a standard, extended biopsy pattern. This practice is consistent with current standard of care in the urological community. The urologist or the participant will have the right to secure a biopsy earlier than 24 months. Although DRE is commonly used in oncologic practice, it is not highly quantifiable for men with the very small, often non-palpable tumors of our study participants.

Blood Sample Submission (12, 24 Months)

Six-hour fasting blood samples will be collected at preregistration, 12 and 24 months and will be submitted to the Alliance Biorepository at Ohio State University (see Section 6.2.1) and analyzed for carotenoid and cholesterol concentrations.

Quality of Life Instruments (Every 6 Months)

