11.3 Analysis

The proportion of men who become ineligible by central pathology review will be estimated for each arm. The primary analysis will be done using data from eligible subjects, especially using Gleason scores from central review. However, all statistical analyses will be conducted for the data sets from eligible patients only, as well as all patients randomized in the sensitivity analysis.

Progression: PSADT will be calculated as \log_2 divided by the slope (the least squares estimator) of \log (PSA) observations over time using all available PSA measurements, starting from the time point at which we have three PSA measurements (i.e. the first

PSADT of a patient is calculated at month 6 using the PSA measurements collected at months 0, 3 and 6 if there are no missing PSA measurements.” In order to avoid any miscalculation, the PSADT will be calculated at the Alliance Statistics and Data Center, not by each individual site.

Time to progression data will be analyzed using the log-rank test for univariable analysis and the Cox’s proportional hazards regression for multivariable analysis adjusting for the stratification factors and other prognostic factors. For the patients who proceed to treatment with surgery, radiation, local ablative therapy or hormonal therapy before progression within the 2-year follow-up period, the progression time will be censored at the time of withdrawal for treatment.

A recent study in a similar cohort of men undergoing active surveillance (102) reported that PSA kinetics was not closely associated with progression on subsequent surveillance biopsies. In order to address this issue, as a secondary analysis, we will also compare time to progression defined only by Gleason sum on repeat biopsy ≥ 7 for men younger than 70 years and $\geq 4+3 = 7$ for men 70 years or older. Because of decreased number of events, the log-rank test using this definition of time to progression may not have enough power. For example, if the 2-year PGR for the control arm is only 10% by this new definition, then the log-rank test will have only 50% of power with 418 eligible patients with events or full 2 years of follow-up.

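### The 5-alpha reductase inhibitor washout is counted back from preregistration, not from the baseline PSA draw, so a PSA taken soon after the last dose can serve as the eligibility value and as the first PSADT point

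*Combined protocol and SAP*

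**What the plan says.** Three rules govern the baseline PSA of a man who has recently stopped one of these drugs.

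- Section 4.1.7 sets the washout and ties it to preregistration: "Patients receiving treatment with 5-alpha reductase inhibitors (e.g., finasteride, dutasteride) within 90 days prior to preregistration are not eligible".
- Section 4.1.11 sets the limit, "Serum PSA < 10 ng/mL", and its note adds: "Baseline PSA for determination of eligibility must be measured after discontinuation of any 5-alpha reductase inhibitors". The note gives no minimum interval.
- Section 7.0 lists "Baseline PSA, history and physical, DRE" under "To be completed within 3 months before preregistration".

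The same value then enters the primary endpoint. Section 8.4 states: "Serum PSA levels will be measured at baseline and at every 3 months thereafter". The calendar in Section 7.0 has one PSA before randomization, in the preregistration column, and the next at month 3. Of the clinic visits it says: "These visits are to be scheduled from the date of randomization". Section 11.3 explains that, if no value is missing, the first "PSADT of a patient is calculated at month 6 using the PSA measurements collected at months 0, 3 and 6". A PSADT under 3 years is progression (Sections 8.7.2 and 11.2), and so is a PSA of 10 or more.

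**The concern.** The note exists because a PSA taken on one of these drugs is not an acceptable baseline. As written it adds almost nothing. A man who satisfies Section 4.1.7 took his last dose by about day -91, which is roughly when the PSA window of Section 7.0 opens, so nearly every draw in that window already follows discontinuation. What would matter is the interval between last dose and draw, and no rule sets it.

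Two consequences are possible, in largely different men. A man whose unsuppressed PSA is below 10 is correctly eligible. If his baseline is still lowered, though, his recovery enters the PSADT regression as growth and can count as progression at month 6. A man whose unsuppressed PSA is 10 or more could pass the eligibility limit and then probably meet the PSA criterion at month 3. Diet would not be expected to prevent either event.

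**Working it through.** **Timing.** Day 0 is preregistration. Section 4.1.7 allows a last dose on day -91. Three calendar months span 89 to 92 days, so Section 7.0 allows a draw on day -90 (day -89 in the shortest case). The draw follows discontinuation, so the note is met. The shortest permitted interval is therefore one day, or two days in the 89-day case. The longest is the full washout or more.

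**Lead time to randomization.** After preregistration, Section 5.4 allows a week before the first dietary recall call and 2 to 3 weeks for the recalls, about one month. A PSA drawn 3 months before preregistration is thus about 4 months old at randomization. The plan does not say whether the regression uses nominal months or draw dates, so both are shown.

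**PSADT.** Section 11.3 defines it as log 2 divided by the least-squares slope of log PSA. Take a man with constant true PSA whose baseline is lowered by a fraction f and whose month-3 and month-6 values are fully recovered.

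- Times 0, 3, 6: deviations from the mean are -3, 0, 3 and their squares sum to 18. Slope = 3 × [-ln(1-f)] / 18 = -ln(1-f)/6. PSADT < 36 months requires 1/(1-f) > 2^(6/36) = 1.122, so f > 10.9%.
- Times -4, 3, 6: deviations are -5.667, 1.333, 4.333 and their squares sum to 52.67. Slope = -ln(1-f) × 5.667/52.67. PSADT < 36 months requires 1/(1-f) > 1.196, so f > 16.4%.

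| Residual suppression f (assumed) | PSADT, months 0, 3, 6 | PSADT, months -4, 3, 6 |
|---|---|---|
| 0% | infinite | infinite |
| 10% | 39.5 months | 61.1 months |
| 15% | 25.6 months | 39.6 months |
| 20% | 18.6 months | 28.9 months |
| 30% | 11.7 months | 18.1 months |

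Section 8.4 uses the last three PSA values and Section 11.3 uses all available values. At month 6 these are the same three values. A longer PSADT at a later visit does not undo a month-6 event in a time-to-event analysis.

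**Eligibility.** A measured PSA below 10 corresponds to an unsuppressed PSA below 10/(1-f): 12.5 ng/mL at f = 20%, 14.3 ng/mL at f = 30%.

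**The plan's own design figure (Section 11.2).** HR = ln(0.80)/ln(0.90) = 2.118, as stated. Freedman's formula with two-sided 5% alpha and 80% power gives 62 events; 62/0.15 = 414, close to the stated 418. At 418 its power is 81.0%.

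**Dilution.** Let a share q of each arm become false events. Control rate = q + (1-q) × 0.20; experimental rate = q + (1-q) × 0.10; HR = ln(1 - control)/ln(1 - experimental). This treats the false events as spread over follow-up, so it is approximate.

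| q (assumed) | Men among 418 | Control | Experimental | HR | Freedman power |
|---|---|---|---|---|---|
| 0% | 0 | 20.0% | 10.0% | 2.12 | 81.0% |
| 1% | about 4 | 20.8% | 10.9% | 2.02 | 78.5% |
| 2% | about 8 | 21.6% | 11.8% | 1.94 | 76.0% |

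**The case against.** The case for leaving the text alone has real substance.

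- The documents do not say how far these drugs lower PSA or how quickly it recovers. The note shows only that an on-drug value is unacceptable. This stands: the gap in the rules is certain, but the false event rests on an assumption.
- One day is the extreme. It needs a last dose just outside the washout and a draw at the far end of the PSA window. Draws nearer preregistration get most or all of the 90 days. This stands too.
- Few men may be affected, and the documents give no count. The values of q are illustrations.
- Ordinary PSA variation may be a larger source of false month-6 events. With constant PSA and an assumed log-scale SD s, the slope has SD s/√18, so the chance of a PSADT below 36 months is about 5% at s = 0.05 and 21% at s = 0.10. Rewording the note would not change that. The drug effect is an additional source, and one that can be removed.

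A reader might infer that one man is both wrongly admitted and then falsely counted by PSADT at month 6. The rules do not support that as the usual course. A man whose unsuppressed PSA is 10 or more would probably meet the PSA criterion at month 3, before any PSADT exists.

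A reader might also infer a bias toward one arm. Allocation is random and the baseline draw precedes it, so the expected effect is dilution in both arms.

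Nothing elsewhere closes the gap. The repeat-draw rule in Section 8.7.2 covers a suspected spurious high PSA, not a falsely low baseline.

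**Conclusion.** The point holds as an inconsistency between Sections 4.1.7, 4.1.11 and 7.0. The washout protects the preregistration date but not the blood draw that decides eligibility and starts the PSADT series. That much follows from the documents alone.

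The effect on the endpoint is conditional. PSA must still be lowered by more than about 11% (nominal months) or 16% (draw 4 months before randomization) in a man with otherwise stable PSA, and must have recovered by months 3 to 6. The share of such men is unknown and probably small. At 1% or 2% the planned hazard ratio of 2.12 would fall to 2.02 or 1.94, a loss of about 2.5 or 5 percentage points of power. This is a cheap improvement, not a threat to the validity of the comparison.

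**What to change.** Reconcile Sections 4.1.7, 4.1.11 and 7.0 so that the sponsor's washout is also defined relative to the baseline PSA draw, not only relative to preregistration. The note should cover both uses of that value: the eligibility limit and the first PSADT point. A PSA drawn inside the washout should be repeated before preregistration and the earlier value not used for either purpose. The sponsor should confirm the interval; nothing in the documents shows what length is sufficient for PSA, and none is proposed here. Section 11.3 should name the draw that counts as month 0.

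The cost is a sentence or two of text, a repeat PSA draw, and possibly a short enrolment delay for the few men who recently stopped such a drug. Nothing changes for anyone else.
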